### **8.3.4 Full Analysis Set (FAS) Immunogenicity Set**

#### **Full Analysis Set Immunogenicity**

All subjects in the All Enrolled Set who receive at least one study vaccination in study V98\_06E1 and provide immunogenicity data at day 1 (pre-vaccination), day 31 or day 61 in V98\_06E1.

### **8.3.5 Per Protocol (PP) Set Immunogenicity Set**

All subjects in the FAS Immunogenicity set who:

- Correctly receive the vaccine (i.e., receive the vaccine to which the subject was randomized and at the scheduled time points) in V98\_06 (for non-naïve subjects).
- Have no protocol deviations leading to exclusion (see [section 8.3.8, Protocol Deviations](#)) as defined prior to analysis.
- Are not excluded due to other reasons defined prior to analysis (see [section 8.3.8, Protocol Deviations](#))

Examples for subjects excluded due to reasons other than protocol deviations are:

- Subjects who withdrew informed consent
- Premature withdrawal due to an adverse event.

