#### **Blood Specimens**

Approximately of 20 mL sample of blood will be drawn from all subjects at visit 1 before vaccination, and at visit 3 and 4. The blood volume will not exceed 25 mL at each time point in order to provide the necessary serum volume (approximately half of the blood draw volume) for the serology assays.

The blood will be used for immunological assays. See [section 7, Assessments](#) for additional details.

The total amount of blood collected over the study period per subject will not exceed 75 mL.

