### **3.8 Premature Withdrawal from Study**

Subjects may withdraw at any time, or be dropped from the study at the discretion of the investigator should any untoward effects occur and/or for safety reasons. In addition, a subject may be withdrawn by the investigator or the Sponsor if she violates the study plan or for administrative reasons. The investigator or study coordinator must notify the Sponsor immediately when a subject has been withdrawn due to an adverse event.

The circumstances above are referred to as premature withdrawal from the study, and the reason for premature withdrawal should be clearly documented and detailed in the source documentation. The investigator should make every attempt to evaluate the subject's safety, including resolution of ongoing AEs, at the time of premature withdrawal. If a subject wants to withdraw from the study before all doses are administered or prior to the last planned study visit, the subject will be asked to be followed for safety for the duration of the study. When a subject withdraws, or is withdrawn, from the study, the procedures described in [section 5.5.1, Early Termination Visit](#) should be completed if possible.

The reasons for premature withdrawal from the study include: Adverse event, death, withdrawal of consent, lost to follow-up, administrative reason, and protocol deviation. These reasons are described in greater detail below.

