## **Withdrawal of consent**

The subject can withdraw consent for participation in the study at any time without penalty or loss of benefit to which the subject is otherwise entitled. Reason for early termination should be deemed as “withdrawal of consent” if the subject withdraws from participation due to a non-medical reason (i.e., reason other than AE). If the subject intends to withdraw consent from the study, the investigator should clarify if the subject will withdraw completely from the study or if the subject will continue study participation for safety, or a subset of other study procedures. If the subject requests complete withdrawal from the study, no further study interventions will be performed with the subject.

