## **Administrative Reason**

Examples for subjects withdrawn from the study due to administrative reason can include: Sponsor decision to terminate the study, subject meeting a pre-specified withdrawal criterion, subject discontinuation for insurance issues, moving, no time, etc. This reason should be noted in the Study Termination CRF page and any ongoing AEs at the time of study withdrawal must be followed until resolution/stabilization.

If the clinical study is prematurely terminated by the Sponsor, the investigator is to promptly inform the study subjects and local EC and should assure appropriate therapy and follow up for the subjects. All procedures and requirements pertaining to the archiving of study documents should be followed. All other study materials (study medication/vaccines, etc.) must be returned to the Sponsor.

For subjects who are withdrawn from the study due to receipt of an excluded medication/vaccination or due to significant protocol non-compliance, this reason should be noted in the Study Termination CRF page.

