#### **8.4.2.3.2 Analysis Sets**

The primary immunogenicity analyses will be based on the per-protocol set (PPS) at day 61. The primary analyses will be repeated using the Full Analysis Set (FAS) as a measure of the sensitivity/robustness of the results (further details are given in [section 8.3](#)).

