##### **8.4.3.3.2 Analysis Sets**

The secondary immunogenicity analyses will be based on the per-protocol set (PPS).

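### Does the undated consent-withdrawal exclusion in section 8.3.5 let a departure after the last blood draw remove valid samples from the per-protocol set?

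*Combined protocol and SAP*

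**What the plan says.** Section 8.3.5 builds the per-protocol set from the full analysis set. It removes subjects with exclusionary deviations and subjects excluded for other reasons settled before analysis. For the second kind it gives two examples: "Subjects who withdrew informed consent" and early departure because of an adverse event. Neither is tied to a visit or a sample. The section refers to 8.3.8, which speaks of removing data, leaves exclusionary deviations to the statistical analysis plan, and names early termination as a non-deviation reason for exclusion.

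On use of the set, section 8.4.2.3.2 states: "The primary immunogenicity analyses will be based on the per-protocol set (PPS) at day 61". It adds a repeat on the full analysis set. Section 8.4.3.3.2 puts the secondary immunogenicity analyses on the per-protocol set, with no time point and no repeat.

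On timing, section 3.5 has blood "drawn from all subjects at visit 1 before vaccination, and at visit 3 and 4". Visits 3 and 4 are days 31 and 61 in Table 3. Calls on days 121 and 181 follow.

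On reasons for leaving, section 3.8 states: "The reasons for premature withdrawal from the study include: Adverse event, death, withdrawal of consent, lost to follow-up, administrative reason, and protocol deviation". Its consent paragraph uses that label for departures on non-medical grounds, meaning other than an adverse event. It also foresees a subject who will "continue study participation for safety, or a subset of other study procedures". The administrative paragraph gives as examples "subject discontinuation for insurance issues, moving, no time, etc".

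**The concern.** Two features together look like a defect in the analysis set.

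First, the exclusion has no cut-off. About two thirds of follow-up comes after the last serum sample, and consent can be withdrawn at any point. Nothing that happens on day 130 can affect serum drawn on days 1, 31 and 61. Yet, read literally at subject level, the example would remove all three samples.

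Second, the category seems open to choice. A woman who stops on day 130 for lack of time fits the consent paragraph of section 3.8, because her reason is non-medical. She also fits the administrative paragraph, which names that very reason. Section 8.3.5 mentions consent withdrawal but not administrative reasons. Two women with identical samples and identical motives might then be treated differently according to the box ticked.

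The analyses exposed would be those planned on the per-protocol set alone: day 31 percentages, GMCs, GMRs, the LLQ subgroups and the anti-diphtheria results. In those no full-analysis-set repeat would show the effect.

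**Working it through.** **Step 1: how much follow-up comes after the last sample.** Day 181 minus day 61 is 120 days, out of 180 (day 181 minus day 1). That is 120/180 = 67%. Only two telephone calls fall in that stretch.

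**Step 2: does the recorded reason decide membership?** Take the day-130 leaver.

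| Recorded as | Example she meets |
|---|---|
| Withdrawal of consent | Consent withdrawal (8.3.5); early termination (8.3.8) |
| Administrative reason | Early termination (8.3.8) |

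Either way she meets a named example, because section 8.3.5 points to 8.3.8. Section 8.3.5 also contains no reference to section 3.8. That its wording means the section 3.8 category, rather than actual revocation of consent, is an inference. The two paragraphs of 3.8 do overlap, but the text does not carry that overlap into the analysis set.

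**Step 3: can the cut-off be applied with planned data?** Section 5.5 has the termination date recorded on the termination CRF page. That date is the day 181 visit, the last contact at which health was assessed, or the date consent was withdrawn if further safety follow-up is refused. Comparing it with the blood-draw date shows which samples came before the departure. A subject who withdraws in part is handled the same way: samples given before are present, and samples not given are absent under the complete-case rule in 8.4.3.3.3.

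**Step 4: size if the literal reading were used.** The plan gives no figure to reproduce. The number of late leavers, the response rates and the SDs are all assumptions. The group sizes of 40 and 20 come from Table 3-1.

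*Day 31 difference against the naive group, Miettinen-Nurminen 95% CI (score method with the N/(N-1) factor). Assumed: 30/40 = 75% against 12/20 = 60%.*

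| Naive group | Difference (points) | 95% CI | Shift from 15.0 |
|---|---|---|---|
| 12/20, none dropped | 15.0 | -9.2 to 40.0 | none |
| 11/19, one responder dropped | 17.1 | -7.7 to 42.4 | 2.1 |
| 12/19, one non-responder dropped | 11.8 | -12.1 to 37.5 | 3.2 |
| 10/18, two responders dropped | 19.4 | -6.1 to 45.0 | 4.4 |
| 12/18, two non-responders dropped | 8.3 | -15.2 to 34.6 | 6.7 |

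The intervals are 49 to 51 points wide.

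*GMC.* Dropping one subject who lies 1 SD above the mean changes the mean log10 by -SD/(n-1), so the GMC is multiplied by 10^(-SD/(n-1)). The half-width factor of an unadjusted one-group 95% interval is 10^(t × SD/√n). It is a guide to scale, not the ANCOVA interval. The log10 SD is assumed to lie between 0.4 and 0.8, and the subgroup of 10 is also assumed.

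| n | GMC multiplied by | Half-width factor |
|---|---|---|
| 40 | 0.977 to 0.954 | 1.34 to 1.80 |
| 20 | 0.953 to 0.908 | 1.54 to 2.37 |
| 10 (LLQ subgroup) | 0.903 to 0.815 | 1.93 to 3.73 |

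In every row the shift is well inside the interval.

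*Day 61 percentage, Clopper-Pearson.* With an assumed 14/20 in the naive group the estimate is 70.0% (45.7 to 88.1). Dropping one subject gives 68.4% (13/19) or 73.7% (14/19). This is the primary endpoint, where the full-analysis-set repeat is planned.

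**The case for a change.** The strongest case for acting is that fixing a list before analysis does not by itself make the list sensible. A list written by recorded reason could still discard day 31 serum because of a day-130 telephone call. The remark about day 61 belongs to the primary analysis and states no withdrawal cut-off, and the secondary analyses lack even that. With no hypotheses, the estimates are the whole output of the study, so a reproducible set definition is a fair thing to ask for, and a sentence would cost almost nothing.

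Part of this stands. No cut-off is written for any of the three examples, and the two paragraphs of section 3.8 do overlap for a subject who leaves on her own initiative for non-medical reasons.

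The claim that a site's choice of label decides membership does not stand, because early termination in 8.3.8 covers both labels. Nor does the claim that the plan discards valid serum: it gives illustrations and leaves the rule to a later step. The existing wording already leans towards handling by time point, since 8.3.8 speaks of removing data and the primary analysis names the set at day 61. Once exclusions follow sampling dates, the overlap in 3.8 has no bearing on the analysis set. It is then only a CRF-coding slip.

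**Conclusion.** No change to the plan is needed. The missing cut-off is a detail that the plan leaves to the definition of exclusions before analysis. Analysts can fill it sensibly from dates that are already collected, keeping samples drawn before a departure unless their use is refused. The overlap between the consent and administrative paragraphs is a clerical matter of reason coding.

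Even on the unfavourable reading, with one or two late leavers all in the smallest group, the illustrated day 31 difference moves by 2.1 to 6.7 points against intervals of 49 to 51 points. One exclusion multiplies a GMC by 0.98 to 0.95 at n = 40 and by 0.95 to 0.91 at n = 20. These figures rest on assumed counts, response rates and SDs.

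The study is descriptive, has no success criterion and repeats its primary analysis on the full analysis set, so no decision turns on the point. The conclusion also assumes that the exclusions are in fact settled before analysis, as section 8.3.5 says. The document reviewed contains no separate detailed list against which to check this.

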### **8.3.6 Other Analysis Sets**

There are no additional analysis sets.

### **8.3.7 Subgroups**

Subgroups of subjects will be created based on the ELISA serotype-specific (Ia, Ib, III) antibody LLQ status prior to initial vaccination in study V98\_06 (or V98\_06E1 for the naive group).

### **8.3.8 Protocol Deviations**

A protocol deviation is any change, divergence, or departure from the study design or procedures of a study protocol. A protocol deviation may be a reason to remove data from an analysis set at the time of analysis. CSR-reportable protocol deviations will be defined as exclusionary from the analysis according to protocol objectives and endpoints, which will be specified in the statistical analysis plan. In some cases exclusion of data may be due to a reason other than a protocol deviation, e.g. early termination.

## **8.4 Statistical Analysis Plan**

### **8.4.1 Analysis of Demographic and Baseline Characteristics**

Descriptive statistics (mean, standard deviation, median, minimum and maximum) for age, height and weight at enrolment will be calculated overall and by vaccine group.

Distributions of subjects by sex, race, ethnic origin, V98\_06 vaccine formulation group (or naïve) and pre-vaccination LLQ status will be summarized overall and by vaccine group.

### **8.4.2 Analysis of Primary Objective(s)**

#### **8.4.2.1 Analysis of Primary Safety Objective(s)**

##### **8.4.2.1.1 Analysis of Extent of Exposure**

The frequency and percentage of subjects with vaccinations in V98\_06E1 will be summarized by vaccine group and overall for the Enrolled Set.

##### **8.4.2.1.2 Analysis of Solicited Local, Systemic and Other Adverse Events**

All solicited adverse events will be summarized according to defined severity grading scales. Use of medication to prevent/treat fever will be summarized according to frequencies and percentages reporting “Yes” and “No”.

Frequencies and percentages of subjects experiencing each adverse event will be presented for each symptom severity. Summary tables showing the occurrence of any local or systemic adverse event overall and at each time point will also be presented.

Post-vaccination solicited adverse events reported from day 1 to day 7 will be summarized for the intervals day 1-3, day 4-7, day 1-7 by maximal severity and by vaccine group, excluding the 30 minute measurement, which will be summarized separately. The severity of solicited local adverse events, including injection-site erythema, swelling and induration will be summarized according to categories based on linear measurement: 0 mm, <25 mm, 25 to 50 mm, 51-100 mm, > 100 mm.

Injection site pain/tenderness and systemic adverse events (except fever) occurring up to day 7 after each vaccination will be summarized according to “mild”, “moderate” or “severe”.

Each solicited local and systemic adverse event will also be further summarized as “none” versus “any”.

Implausible measurements (for further definition see statistical analysis plan) will be left out of the analysis.

Use of antipyretics and analgesics will be summarized by frequency, by type of use (prophylactic versus treatment), and percentage of subjects reporting use.

Body temperature will be summarized by 0.5 °C and 1.0 °C increments from 36.0 °C up to  $\geq 40$  °C and will be broken down according by route of measurement.

#### **8.4.2.1.3 Analysis of Unsolicited Adverse Events**

This analysis applies to all adverse events occurring during the study, judged either as probably related, possibly related, or not related to vaccination by the investigator, recorded in AE CRF, with a start date on or after the date of first vaccination. AE starting prior to the first vaccination will only be listed. The original verbatim terms used by investigators to identify adverse events in the CRFs will be mapped to preferred terms using the MedDRA dictionary. The adverse events will then be grouped by MedDRA preferred terms into frequency tables according to system organ class.

All reported adverse events, as well as adverse events judged by the investigator as at least possibly related to study vaccine, will be summarized according to system organ class and preferred term within system organ class. These summaries will be presented by vaccination group. When an adverse event occurs more than once for a subject, the maximal severity and strongest relationship to the vaccine group will be counted.

Separate summaries will be produced for the following categories:

- Serious adverse events.
- Adverse events that are possibly or probably related to vaccine.
- Adverse event leading to withdrawal.
- Adverse events leading to a medically attended visit.

Data listings of all adverse events will be provided by subject. In addition, adverse events in the categories above will be provided as listed data.

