**Table 2 Study Procedures**

Vaccine Group	Visit for Vaccination	Subject Diary Reminder calls (To remind the subject to fill out the Subject Diary)	Visits for Blood Sampling for Immunogenicity	Safety Follow-up calls
Lyophilized GBS Trivalent Vaccine, 5µg of each glycoconjugate (serotype Ia/Ib/III), unadjuvanted	Day 1	Day 3 Day 5	Day 1 (pre- vaccination), Day 31 and Day 61	Day 15 Day 121 Day 181

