#### Safety Objective

To assess the safety and tolerability of a second dose of GBS Trivalent Vaccine (5 µg without adjuvant) administered approximately 4-6 years after the initial dose.

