#### *Geometric Mean Ratios*

The logarithmically (base 10) transformed within subject ratio of antibody concentrations (post vaccination / baseline) will be modeled using an analysis of variance model with a qualitative factor for vaccine group (vaccine received in study V98\_06 or naïve). The

adjusted GMR and the two-sided, 95% CIs of the GMR will be calculated based on this model. The model can be written as:

$$\log_{10}(y_{ik}) = \mu + \alpha_i + \varepsilon_{ik}$$

where  $\mu$  represents a common overall mean,  $\alpha_i$  represents the vaccine group  $i$  effect and  $\varepsilon_{ik}$  represents random error for subject  $k$  in vaccine group  $i$ . The baseline value is either the pre-vaccination concentration in study V98\_06 or the pre-vaccination concentration in study V98\_06E1 as both are to be used in separate analyses. A similar approach will be used in the subgroups based on pre-vaccination LLQ status.

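### Does the safety analysis need a pooled adverse-event column for the second-dose arms, and its own definition of vaccine group?

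*Combined protocol and SAP*

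**What the plan says.** The Safety Objective in section 2.1 reads in part "To assess the safety and tolerability of a second dose of GBS Trivalent Vaccine". Table 3-1 lists six groups: four V98_06 arms that had a single 5 µg dose (no adjuvant, Alum, MF59 full dose, MF59 half dose), the V98_06 placebo subjects, and naive subjects. All receive the same unadjuvanted product in this study.

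The adverse-event tables are split by group. Section 8.4.2.1.2 presents solicited events "by maximal severity and by vaccine group". Section 8.4.2.1.3 says of unsolicited events "These summaries will be presented by vaccination group". Neither subsection says what the groups are or names a column for all second-dose recipients.

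Elsewhere the term is used as follows:

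- Section 8.4.3.3.3, Geometric Mean Ratios, has a "qualitative factor for vaccine group (vaccine received in study" V98_06, or naive. The Geometric Mean Concentrations model in the same section says the same.
- Section 8.4.2.1.1, itself part of the safety analysis, says exposure "will be summarized by vaccine group and overall for the Enrolled Set".
- Section 8.4.1 lists V98_06 formulation group among the baseline variables and says that these and "pre-vaccination LLQ status will be summarized overall and by vaccine group".
- Synopsis Table 2 has a column headed with the term and a single row, the product "of each glycoconjugate (serotype Ia/Ib/III), unadjuvanted".
- Section 8.4.2.1.3 also says that, for repeated events, "the maximal severity and strongest relationship to the vaccine group will be counted".

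**The concern.** The objective asks one question: how well is a second dose tolerated? The subjects who can answer it sit in four arms of at most 40, and no planned table gives a single second-dose figure or one pooled comparison of second-dose with first-dose recipients. For immunogenicity, by contrast, section 8.4.2.3 does plan pools: the MF59 arms, the unadjuvanted and Alum arms, and placebo with naive.

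The undefined term adds to the doubt. If vaccine group meant the product given in this study, every adverse-event table would have one column of up to 220 subjects, and up to 60 of them would be receiving a first dose. That column would mix the population named in the objective with its comparator. Three places could be read that way: the single row in synopsis Table 2, the phrase about relationship to the vaccine group in 8.4.2.1.3, and the rule in section 8.3.3 that safety subjects are analysed by the vaccine received.

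**Working it through.** **1. The groups.** From Table 3-1: 5 × 40 + 20 = 220, which reproduces the stated maximum. Second-dose recipients: 4 × 40 = 160. First-dose recipients: 40 + 20 = 60.

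**2. What vaccine group means.** There are two candidates.

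*Six groups (V98_06 arm, or naive).* The two model descriptions in 8.4.3.3.3 say this outright. Section 8.4.2.1.1 pairs by vaccine group with overall, as does 8.4.1, and that pairing has no purpose if there is only one group. The design is described as parallel-group. The synopsis lists the individual groups as analysis groups just before its sentence on safety analyses.

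*One group (the product given here).* The support is thin:

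- The entry in synopsis Table 2 is a column header in a visit schedule.
- The phrase in 8.4.2.1.3 concerns an event's causal relationship to vaccination, so it is loose wording for the study vaccine and does not define table columns.
- The as-treated rule in 8.3.3 sets a principle for assigning subjects and names no columns.
- The 8.4.1 listing of formulation group by vaccine group is redundant under the six-group reading, but it still informs the overall column.

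The six-group reading is clearly better supported.

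**3. What the tables then show.** Each row has four second-dose columns, a placebo column and a naive column. First-dose subjects do not enter the second-dose columns. Both kinds of recipient appear side by side in every table.

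**4. Whether information is lost.** Let x₁ to x₄ be the subjects with the event in the four arms and n₁ to n₄ the denominators. The pooled second-dose percentage is

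(x₁ + x₂ + x₃ + x₄) / (n₁ + n₂ + n₃ + n₄).

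The arms are disjoint. Each subject is counted once per row, at maximal severity or as any versus none, so the sum is exact. The same holds for placebo plus naive.

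**5. The burden of adding.** Section 7.1.1 lists 6 local and 8 systemic reactions, 14 in all. Section 8.1.1.1 gives 4 intervals. That makes 14 × 4 = 56 rows for any reaction, and 56 × 4 = 224 cells to add across the four arms, before severity grades. This is clerical work on published counts.

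**6. Precision.** With zero events, the exact two-sided 95% upper limit is 1 − 0.025^(1/n): 8.8% at n = 40 and 2.3% at n = 160. The gap is real, but the plan calls for no adverse-event intervals, and extra count columns would not produce any. A reader who wants the 160-subject limit can compute it from the summed counts.

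**The case for a change.** The strongest case for a change is that the quantity named in a primary objective should be specified in advance and not left for readers to assemble. A definition and two columns would cost almost nothing and use data already collected. Pooling is not foreign to this plan, since the immunogenicity analysis pools across first-dose adjuvants. Loss to follow-up, which the protocol expects, may leave single arms well below 40.

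The single-column reading, if followed, would do real harm. First-dose subjects would make up 60/220 = 27% of the column, or 40/120 = 33% if half of each V98_06 group returned and naive stayed at 20. With assumed event rates of 30% after a second dose and 15% after a first, the column would show (0.30 × 160 + 0.15 × 60)/220 = 57/220 = 25.9%.

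What stands: section 8.4.2.1 does not restate the definition, the wording is loose in places, and no pooled column is planned. A sentence of definition would be tidier. What does not stand is that the plan would mislead or leave the question unanswered. The dilution needs a reading that the plan's own definitions contradict. A pooled rate would also average over different first-dose adjuvants, weighted by which arms happen to return, and section 1.2 names those adjuvants as a source of baseline heterogeneity. Showing safety by arm is therefore a defensible choice.

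**Conclusion.** No change to the plan is needed. Read with its own definitions, it gives sound by-arm adverse-event tables in which second-dose and first-dose recipients are already separate, and the pooled second-dose count follows exactly by addition. Section 8.2 sets no success criterion and section 8.5 no power basis, so no decision turns on a pooled column. The missing definition is a detail that analysts would fill correctly from section 8.4.3.3.3 and Table 3-1, and the pooled columns are a matter of layout.

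This rests on one assumption: that vaccine group has the same meaning in the safety tables as in the immunogenicity models. Sections 8.3.8 and 8.4.2.1.2 also refer to a statistical analysis plan for further detail. The text reviewed here contains no separate one, and the conclusion does not depend on it.
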